**Supporting Refugee and Immigrant Youth's Mental Health: Examining Effectiveness and Implementation of a
School-Based Intervention**

NCT05208359

02/14/2025

STRONG will be implemented in six public schools during 2021-2022 academic year and six public schools during the 2022-2023 academic year. We anticipate three elementary schools and three high schools each year. Within CPS, school leadership has requested interventions specifically designed for refugee and immigrant students due to school population and need. In each school, one group of approximately five students will be implemented. Schools will be randomly assigned to either provide the STRONG program immediately (immediate treatment) or after three months (delayed treatment). Randomization will include balancing of elementary and high schools so that the number of elementary and high schools randomized to immediate vs. delayed treatment will be equivalent. School mental health staff (e.g., district-employed social workers or community clinicians who provide services in schools) will co-facilitate groups in schools, meeting once a week. School-based clinicians are typically expected to deliver one to two small group interventions as part of their job duties. District partners have committed to supporting clinicians in delivering STRONG as part of this expectation. The research team, comprised of 10 undergraduate students and four graduate students, will collect data at baseline and then at three- and six-months post baseline. Undergraduate and graduate student pairs will meet with students and parents at schools allowing for support and mentorship of undergraduate research assistants along with clinical expertise from graduate students enrolled in the Clinical Psychology PhD program at Loyola University Chicago.

Eligibility Criteria

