graduation celebration. Between sessions four and eight, students meet individually with the clinician to discuss their journey to the U.S. This may include positive and difficult experiences, including potential traumatic experience. The clinician guides students to recognize strengths that helped them get through their journey rather than focusing on a single event with repeated retelling. The journey narrative is flexible to allow students to discuss multiple traumatic experiences, while also highlighting strengths and assets. It is recommended that the clinician screen for significant PTSD symptoms in individual sessions to consider if additional referrals will be necessary after STRONG. Clinicians also have individual sessions with caregivers and teachers to provide psychoeducation on the children's participation in the STRONG program. This allows for caregivers and teachers to support the student's progress in multiple settings (Hoover et al., 2019).

Participants

An estimated 60 students will participate in STRONG (five students per group across six public schools over two years). Student age range will be 8-18, though each STRONG group will be comprised of students within one grade level of each other. Clinicians, school personnel (teachers, administrators), and parents will be invited to complete measures and participate in focus groups (clinicians) or interviews (teachers, administrators). Teachers who have students participating in STRONG and/or assisted with referrals/identification of students will be recruited to participate in interviews. Teacher participants will be identified in collaboration with school partners/administrators. For example, English Language Learner (ELL) teachers have been key partners in referrals/identification of students in our preliminary feasibility pilot.

Procedure

Clinicians will identify eligible students and reach out to parents/caregivers consistent with standard school procedures. Clinicians will offer a group or individual information meeting to share more about STRONG and will ask parent permission to share contact information with the research team. With permission, the research team will meet with parents as part of the informational meeting or at a later date to provide additional information about the research protocol and obtain informed consent and assent.

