School Connectedness. Students will complete the School Connectedness Scale at each assessment. This 5-item scale was adapted from the Add Health study that measures students' bond towards their school (e.g., "I feel like I am part of this school"; McNeely et al., 2002; Furlong et al., 2011). Students will complete the School Climate subscale of the California Healthy Kids Survey (CHKS; WestEd, 2000) to assess school relationships and support (9 items; e.g., "At my school, there is a teacher or some other adult who really cares about me"). Students will rate the items on a rating scale from 1 (*Not at all true*) to 4 (*Very much true*).

Fidelity, & Student Engagement. Clinicians will complete a fidelity checklist for each session indicating whether core content was covered on a scale ranging from 0 (*Not at all*) to 3 (*Thoroughly covered*), with the specific items varying by session. Clinicians will additionally identify challenges, activities that were well received, and amount of time per session. Clinicians will rate students' engagement and current functioning during each session.

Satisfaction. After STRONG implementation, clinicians will respond to six items (e.g., implementation challenges, satisfaction with training) and parents will rate four items (e.g., benefits of the program, importance of the program) on a five-point scale from *Not at all* to *A whole lot*. Children will rate how much they liked the STRONG curriculum on a three-point scale from *Not at all* to *Very much*.

Analytic Strategy

Quantitative and qualitative methods will be utilized at various stages of the study. Intent to treat analyses will be conducted, and imputation approaches will be considered. Pre-treatment group differences will be included as covariates in analyses, as appropriate. Outliers and assumptions of normality will be examined and transformations considered. Consultation with [name] and [name] will include discussion of data analyses. See Figure 1 (also shown in Specific Aims) for conceptual model guiding Aims 1 & 2.

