Aim 1. To test the hypotheses that students who participate in STRONG will show improvements in self-reported, parent-reported, and teacher-reported mental health (emotional symptoms, conduct problems, hyperactivity/inattention, and peer problems) as compared to the waitlist control group, repeated measures Analyses of Variance (ANOVA) will be conducted (***Aim 1, Hypothesis 1***). Repeated measures ANOVAs will be conducted on the primary mental health variables (total difficulties, emotional symptoms, conduct problems, hyperactivity/inattention, and peer problems) from baseline to post-treatment to test for a significant Time X Group interaction. Power analyses conducted with GPower (Faul et al., 2006) indicate that a sample size of N=54 is required to detect a Time X Group interaction with a medium effect using two time-points and N=44 utilizing all three repeated measures, suggesting adequate power.

Aim 2. To test the hypotheses that students who participate in STRONG will show improvements in self-reported resilience, coping efficacy, school connectedness and parent-reported coping (***Aim 2, Hypothesis 1***), repeated measures ANOVAs will be conducted on resilience, coping, and school connection from baseline to post-treatment to test for a significant Time X Group interaction. To test the hypothesis that these changes will be related to student mental health improvement/maintenance over time (***Aim 2, Hypothesis 2***), hierarchical linear modeling (HLM) will be utilized. HLM analyses (repeated measures nested within individuals) will allow for an examination of how changes over time on intervention targets (resilience, coping, and school connection) predict student mental health trajectories across all three time-points for the immediate treatment group. This approach is ideal for nested data and capitalizes on all existing time points.

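### Cheap improvement: in Aim 1 and Aim 2 H1, replace the raw-change test and open covariate rule with each 3-month score adjusted for its own baseline, with a school random effect

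*Combined protocol and SAP*

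**What the plan says.** The Analytic Strategy gives one covariate rule for all quantitative analyses: "Pre-treatment group differences will be included as covariates in analyses, as appropriate". It lists no variables and sets no threshold for a difference.

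Aim 1 applies repeated measures ANOVA to five SDQ variables "from baseline to post-treatment to test for a significant Time X Group interaction". With self, parent and teacher report that makes 5 x 3 = 15 tests. Aim 2 Hypothesis 1 uses the same method: "repeated measures ANOVAs will be conducted on resilience, coping, and school connection from baseline to post-treatment". Neither names a covariate. Each outcome's baseline enters as the first of the repeated measures.

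The power statement under Aim 1 says "N=54 is required to detect a Time X Group interaction with a medium effect using two time-points and N=44" with all three waves. It does not give alpha, power, the correlation between waves or the numerical effect size.

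Schools are the randomised unit. The opening study description says "Randomization will include balancing of elementary and high schools", but school level appears in no analysis. That description has "six public schools during 2021-2022 academic year and six public schools during the 2022-2023 academic year", and also "We anticipate three elementary schools and three high schools each year". The Participants section has "five students per group across six public schools over two years".

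**The concern.** With two waves, the Time X Group test is a t-test on change scores. Subtracting the whole baseline score is efficient only when the pre-post correlation is close to 1. At lower correlations it adds baseline noise that regression on baseline would remove. The data for the better estimator are already being collected.

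Precision is scarcest for self-report. The Measures section limits it to students aged 11 and over, so if 8- to 10-year-olds enrol, fewer than 60 students contribute. In addition, the covariate set is settled only after baseline differences are seen, and it may differ across the 15 Aim 1 tests.

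**Working it through.** **Inputs.** From the plan: 60 students, N=54 and N=44, a medium effect, randomisation by school. Assumed: f=0.25, alpha 0.05, pre-post correlation rho, ICC, stability of school effects between waves (half or full), and a self-report N of 30-40.

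**1. The plan's own figures.** Noncentral F with lambda = f^2 N m/(1-rho) and df (m-1) and (N-2)(m-1). At rho 0.5:
- m=2, N=54: lambda = 0.0625 x 54 x 2/0.5 = 13.5, power 95.0%.
- m=3, N=44: lambda = 0.0625 x 44 x 3/0.5 = 16.5, power 95.6%.

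Both Ns reproduce. The same pair also arises at rho 0.175-0.20 (80% power), 0.28-0.30 (85%) and 0.385-0.40 (90%), so the documents do not fix rho.

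**2. Implied effect.** For a difference D in change, lambda = N D^2/[8(1-rho)]. Setting this equal to 2 f^2 N/(1-rho) gives D = 4f = 1.0 SD.

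**3. Precision without clustering.** Variance is 2(1-rho) for change and 1-rho^2 after adjustment. The ratio is (1+rho)/2, so the cut is (1-rho)/2: 40%, 25% and 15% at rho 0.2, 0.5 and 0.7. Power, change to adjusted:

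| N and effect | rho 0.2 | rho 0.5 |
|---|---|---|
| 60, 1.0 SD | 85 to 97% | 97 to 99% |
| 40, 1.0 SD | 68 to 88% | 87 to 94% |
| 30, 1.0 SD | 55 to 77% | 75 to 86% |
| 60, 0.5 SD | 33 to 49% | 48 to 59% |

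**4. Type I error if the school effect is left out** (simulation, 12 schools of 5, stable school effects). A stable school effect cancels in a change score but is only partly removed by regression on baseline. The plan rejects about 5%. The adjusted model rejects 6.4-8.6% at ICC 0.10 and 8.7-11.8% at ICC 0.20 (rho 0.2-0.5). A separate 8,000-run simulation gave 5.0-5.4% for the plan, against 6.3-8.7% and 8.1-12.2%. If school effects are only half stable, the two analyses are about equal at rho 0.5, and the adjusted one is 1-2 points worse at rho 0.2 with ICC 0.10-0.20.

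**5. School random effect in both models** (12 x 5, 4,000 runs per effect size, school-level df). The adjusted model here also carries school level. Variance falls about 12-37% at ICC 0.05-0.10 and rho 0.2-0.5, and 6-16% at rho 0.7. At ICC 0.20 it falls 16-31% if school effects are half stable; if fully stable, there is no gain or a loss of up to about 4%. Rejection at 1.0 SD, ICC 0.05-0.10:

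| Analysis | rho 0.2 | rho 0.5 | Type I error |
|---|---|---|---|
| Plan, unclustered | 83-85% | 95-97% | 4-10% |
| Change, school effect | 67-74% | 83-92% | not reported |
| Adjusted, school effect | 84-89% | 91-96% | 2.5-4% |

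A second computation with school-level inference in both models gave 67-80 to 86-92% (rho 0.2) and 84-94 to 93-97% (rho 0.5).

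**6. School level.** No benefit was found. The term costs 0-2 points of power with 12 schools split 3:3 by level, and about 3-6 points if the two years end 4:2. Three schools per level cannot be split equally within one year.

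**7. Six schools of 10** (rho 0.5, 1.0 SD). Power for change / baseline only / baseline and level: 77/79/62% at ICC 0.10 with stable effects, 55/67/50% at ICC 0.10 with half-stable effects, and 77/67/51% at ICC 0.20 with stable effects.

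**8. The covariate rule itself.** Adjusting only when baseline differs at p<0.05 gives a simulated type I error of 4.0-4.7% without clustering.

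Simulation error is 1-2 points for power and a few points for variance cuts.

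**The case against.** The plan already uses each outcome's baseline, its test is unbiased here, and change score against covariance adjustment is an efficiency choice. At rho 0.5, N=60 and the implied 1.0-SD effect, the gain is only 97 to 99%. Larger gains need a lower rho, a smaller effect or an assumed self-report N. All of this stands, and it is why the point is an improvement and not a correction of an error.

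Two stronger readings are tempting.

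- A reader might infer that the open covariate rule inflates type I error. Simulated inflation to about 7-8% appears only if the analyst keeps the smaller of the unadjusted and adjusted p-values. The plan ties inclusion to pre-treatment differences, not to outcome results, and a mechanical version of that rule is slightly conservative.
- A reader might infer that school level must be in the model because randomisation balanced it. That is a defensible convention, but no figure here shows a gain, and with six schools it costs power.

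It is also fair to object that baseline adjustment alone can damage the test. It can, as step 4 shows, so the school effect has to be part of the same change.

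**Conclusion.** The point holds as a cheap gain in precision. The planned analysis is not invalid on this point, and the stated Ns are not shown to be wrong. Without clustering, adjustment for own baseline cuts variance by 40%, 25% or 15% at rho 0.2, 0.5 or 0.7.

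Once a school effect is included, the adjusted analysis does not clearly have more power than the unclustered plan, whose type I error can reach about 10%. Against a change analysis that also respects school randomisation, it recovers most of the lost power at ICC 0.05-0.10 with 12 schools. There is little or no gain, or a small loss, if the ICC is about 0.20 and school effects are fully stable. With six schools in that case, even baseline-only adjustment can lose power (77 to 67%). Rho, ICC, stability and self-report N are all assumptions, because the documents give none of them.

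**What to change.** Replace the covariate sentence in the Analytic Strategy, and align Aim 1 and Aim 2 H1 with it:

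*For each Aim 1 and Aim 2 H1 outcome, the 3-month score will be modelled on arm and that outcome's own baseline score, with a random effect for school and small-sample (school-level) degrees of freedom. This set is the same for every outcome, and adjustment for other observed pre-treatment differences is a sensitivity analysis only.*

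The 3-month score is the one to use because, under Procedure, the delayed arm has been treated by six months.

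Two matters need settling first:
- Reconcile the opening description and the Participants section on the number of schools. Add school level only if 12 distinct schools take part.
- Table 3 lists randomisation before the baseline assessment. Confirm that baseline is obtained before allocation is disclosed to raters; otherwise report the change analysis beside the adjusted one.

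The cost is SAP wording and that confirmation. No new data are needed.

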Immediate Treatment						
Group formation	Consent; Randomization ; Baseline/Pre-Treatment Assessment	STRONG Group	Post-Treatment Assessment	Wait Period (No Treatment)	Repeated Post-Treatment Assessment	Data entry & scoring; Preparation for analyses
Delayed Treatment						
Group formation	Consent; Randomization ; Baseline Assessment	Waitlist (No Treatment)	Repeated Baseline Assessment	STRONG Group	Post-Treatment Assessment	
YEAR 3: FALL		WINTER		SPRING		SUMMER
Finish Quantitative Analyses; Code Qualitative Data		Finish Coding Qualitative Data and Conduct Thematic Analysis; Begin preparation for publication		Share findings with partners; Plan future implementation/dissemination; Submit findings for publication; Prepare R01 grant application		

Student Mental Health. Parents, teachers, and students will complete the Strengths and Difficulties Questionnaire (SDQ), a 25-item measure that assesses mental health functioning (Goodman, 1997). It includes a Total Difficulties score and four problem subscales: hyperactivity/inattention scale (e.g., "Restless, overactive, cannot stay still for long"); the emotional symptoms scale (e.g., "Often unhappy, down-hearted or tearful"); the conduct problems scale (e.g., "Generally obedient, usually does what adults request"); the peer problems scale (e.g., "Generally liked by other children"). It also has a prosocial scale (e.g., "Considerate of other people's feelings"). Teachers will complete the SDQ based on their observations of students within their classrooms. Parents will complete the SDQ based on their observations of their child at home. Students will self-report on their mental health. Respondents rate statements on a 3-point scale from *Not true* to *Certainly true*. The SDQ is available in a number of languages including Arabic, Spanish, and Urdu.

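### Schools are randomised, but the Aim 1 and Aim 2 Hypothesis 1 ANOVAs carry no school term and the sample sizes treat students as independent; if change correlates positively within schools, the Time X Group test is anti-conservative

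*Combined protocol and SAP*

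**What the plan says.** The overview makes the school the unit of allocation: "Schools will be randomly assigned to either provide the STRONG program immediately (immediate treatment) or after three months (delayed treatment". On cluster size it says "In each school, one group of approximately five students will be implemented". It plans six schools in each of two years, and "We anticipate three elementary schools and three high schools each year". Allocation is balanced so that "the number of elementary and high schools randomized to immediate vs. delayed treatment will be equivalent". Staff "will co-facilitate groups in schools, meeting once a week". The Participants section gives 60 students but describes them as "five students per group across six public schools over two years", which can be read as six schools in total. Table 3 lists "Consent; Randomization ; Baseline/Pre-Treatment Assessment" in both years.

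Under Analytic Strategy, for Aim 1, "repeated measures Analyses of Variance (ANOVA) will be conducted" to test the Time X Group interaction, and Aim 2 Hypothesis 1 uses the same method. Neither names a school effect, a cluster-robust variance, an ICC or a design effect. The power statement gives N=54 (two time-points) and N=44 (three) for a medium effect and concludes that power is adequate. It does not state alpha, target power or the correlation between occasions. The only multilevel model is for Aim 2 Hypothesis 2; it nests occasions within students, in the immediate group alone.

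**The concern.** The randomised contrast compares sets of schools. Students in one school share a setting and, once treated, a group and its co-facilitators, so their changes may be correlated. A repeated measures ANOVA on 60 students uses 60 - 2 = 58 error degrees of freedom at two waves. Twelve schools in two arms supply 12 - 2 = 10, or 12 - 4 = 8 once school level and year are fitted. With positive correlation of change, the standard error is too small.

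The relevant correlation is that of change: stable differences in level between schools cancel in the Time X Group test. What is at stake is the error rate of the trial's only randomised comparison, on every Aim 1 and Aim 2 Hypothesis 1 outcome, and the basis for calling 60 students enough. The Aim 2 Hypothesis 2 model is not part of this point.

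**Working it through.** **1. Reproduce 54 and 44.** Take independent students, two groups, and assume f = 0.25 for a medium effect and alpha 0.05. The within-between interaction has noncentrality lambda = N x m x f^2 / (1 - rho), with (m - 1) and (N - 2)(m - 1) df, where m is the number of waves. The smallest even N is exactly 54 at two waves and 44 at three for each of four pairs of correlation and target power: 0.2/0.80, 0.3/0.85, 0.4/0.90 and 0.5/0.95. For the last pair, lambda = 54 x 2 x 0.0625 / 0.5 = 13.5 gives power 0.950, and N = 52 gives 0.942. So the figures are independent-student figures, and their inputs cannot be recovered uniquely.

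**2. Effective sample size.** From the overview, 12 schools x 5 = 60 if Year 2 uses different schools. The design effect is 1 + (5 - 1) x ICC.

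- ICC 0.05: 60/1.2 = 50
- ICC 0.10: 60/1.4 = 43
- ICC 0.20: 60/1.8 = 33

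Effective N drops below 54 when ICC exceeds (60/54 - 1)/4 = 0.028, and below 44 when it exceeds (60/44 - 1)/4 = 0.091. These thresholds need no assumption about rho.

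**3. Type I error.** At two waves the Time X Group F test equals a t test on change. Null simulations used 200,000 trials per cell, 12 schools x 5, 58 df, nominal 5%, at assumed ICCs of change:

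| ICC of change | Both arms cluster | Treated arm only | Both arms, levels differ by 0.5 SD in mean change |
|---|---|---|---|
| 0 | 5.0% | 5.0% | 4.3% |
| 0.05 | 7.3% | 6.2% | 6.5% |
| 0.10 | 9.9% | 7.3% | 8.9% |
| 0.20 | 14.7% | 10.0% | 13.5% |

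The large-sample formula 2 x [1 - Phi(1.96 / sqrt(design effect))] gives 7.4%, 9.8% and 14.4% for the first column at ICC 0.05, 0.10 and 0.20. A t test on school means stays at 4.9 to 5.2%. The last column reflects balancing 3 v 3 within each level: the level difference cancels in the contrast but, with no level term, inflates the residual variance.

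**4. Power of a model that respects the design.** The variance of change is proportional to 2(1 - rho), and that of a baseline-adjusted outcome to (1 - rho^2), so adjustment multiplies lambda by 2/(1 + rho). With N = 60 and two waves, lambda = 9.375 at rho 0.2 and 15 at rho 0.5. Idealised power on 8 df, with noncentrality lambda x 2/(1 + rho) / (1 + 4 x ICC), at ICC 0, 0.05, 0.10 and 0.20:

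- rho 0.2: 0.932, 0.883, 0.832, 0.733 (planned 58-df test, independent students: 0.853)
- rho 0.5: 0.973, 0.945, 0.910, 0.830 (planned: 0.968)

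Here ICC is that of the baseline-adjusted residual. This differs from the ICC of change because adjustment with a slope below 1 does not fully remove stable school differences. In a simulation with zero ICC of change and a stable school variance of 10% of the total, a baseline-adjusted student-level test without a school term rejected 8.2% (rho 0.2) or 6.6% (rho 0.5).

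**5. Where 12 x 5 does not apply.** The Measures section collects no self-report at ages 8-10, so self-report outcomes have fewer students and possibly fewer schools. If the same six schools recur, the cluster count, cluster size and df change. With one allocation held for both years and ten students per school, the design effect is 1 + 9 x ICC, and effective N is 41, 32 and 21 at the three ICCs.

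**The case against.** The strongest reply is that the ICC of change is unknown and may be near zero, in which case the planned test keeps its 5%. That stands, and the error-rate claim is conditional on it. But the plan neither estimates the ICC nor protects against it, and shared groups and facilitators make a positive value plausible.

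Second, balancing by school level pulls the error rate down if elementary and high schools change differently. This also stands: the reduction is modest at a 0.5 SD difference and larger at 0.8 SD (about 5.4% and 7.5% at ICC 0.05 and 0.10). It does not remove the problem across the range.

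Third, the Analytic Strategy allows covariates for pre-treatment differences and consultation on the analyses. Neither is a school adjustment, and a student-level covariate does not correct the standard error of a school-randomised contrast.

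A reader might go further and infer that the trial is underpowered. The documents do not support that. Target power, correlation and ICC are all unstated, and on the inputs in step 4 a baseline-adjusted school-level model can have more or less power than the planned test.

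**Conclusion.** The analysis does not match the unit of randomisation, and the sample sizes carry no allowance for it. For parent and teacher outcomes with 12 distinct schools of five, no school-level effect on change, and an ICC of change between 0.05 and 0.20, the nominal 5% test runs at about 7% to 15% if both arms cluster and about 6% to 10% if only the treated arm does. It runs at 5% if the ICC is zero. The ICC values are assumptions. The same figures should not be carried over to self-report outcomes or to a design with six recurring schools. The claim of adequate power is unsupported rather than refuted. This should be corrected before the randomised comparison is reported, because a positive result could not be taken at its nominal level.

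**What to change.** For Aim 1 and Aim 2 Hypothesis 1, make the primary analysis a linear mixed model of the three-month outcome adjusted for baseline, with arm, school level and year as fixed effects, a school random effect and pre-specified small-sample degrees of freedom. These are 8 if 12 distinct schools contribute, and should be recomputed for each outcome otherwise.

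As a check, add a permutation test that reassigns whole schools under the constraints actually used, and state those constraints: with three schools per level each year, exact balance within a year is impossible. For example, if each year is 3 v 3 and the 2/1 level split is reversed in Year 2, there are 9 x 9 x 2 = 162 allocations and the smallest two-sided p is 2/162 = 0.012.

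Reconcile the overview and the Participants section on the number of distinct schools. Restate the power line for this model: target power, effect size, correlation, number of schools, expected self-report N, and a design effect 1 + (m - 1) x ICC, with m students per school, over a stated range such as 0.02 to 0.20. The ICC should be that of the baseline-adjusted residual.

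The cost is SAP wording and slightly more analysis, with no new students or data. The fixed-df test is conservative when clustering is small (about 2% type I error at ICC 0 in 20,000 simulated null trials), which would lower actual power below the idealised figures. Net power may be lower or higher than planned, since baseline adjustment offsets some of the loss from clustering and fewer degrees of freedom.

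### Schools are randomised separately in each of two academic years, but the Time X Group tests have no year term; a minor, cheap gap whose effect depends on how the arms fell within each year

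*Combined protocol and SAP*

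**What the plan says.** The opening design description states that "STRONG will be implemented in six public schools during 2021-2022 academic year and six public schools during the 2022-2023 academic year". It adds "We anticipate three elementary schools and three high schools each year". Schools are the unit of allocation, to immediate treatment or treatment delayed by three months. The only balancing factor named is school level: "Randomization will include balancing of elementary and high schools", with the aim that the numbers of each kind in the two arms be equivalent. Year is not mentioned as a factor.

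Table 3 repeats the allocation step in Year 2. The immediate-treatment row lists "Consent; Randomization ; Baseline/Pre-Treatment Assessment" and the delayed-treatment row lists "Consent; Randomization ; Baseline Assessment".

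Under Analytic Strategy, Aim 1, "Repeated measures ANOVAs will be conducted on the primary mental health variables", from baseline to post-treatment, with the Time X Group interaction as the test. Aim 2 Hypothesis 1 uses the same test for resilience, coping and school connection. Neither paragraph has a term for year or cohort. The opening paragraph of Analytic Strategy allows adjustment for baseline differences between the arms where this is judged suitable, without naming any variable.

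Pooling is not stated but is implied. Five students in each of six groups gives about 30 students per year, against a stated need of 54 (two time-points) or 44 (three).

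**The concern.** If allocation is carried out afresh each year, year is a block of the randomisation, and the analysis would normally carry it. Students' change over three months may differ between the two school years for reasons unrelated to STRONG. When that term is missing, one of two things happens to the year difference:

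- If the immediate:delayed split differs between years, part of the year difference appears as a treatment effect, in either direction.
- If the split is the same in both years, the year difference stays in the residual and widens the standard error.

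The first matters more, because it moves the estimate for every outcome tested under Aim 1 and Aim 2 Hypothesis 1. Whether it can occur turns on whether the plan guarantees the same split in both years.

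**Working it through.** **1. The plan's own sample size.** The document gives a medium effect and N = 54 / 44, but no alpha, power or correlation. Assume f = 0.25, alpha 0.05, correlation 0.5 and two groups. The noncentrality is lambda = f² × N × m / (1 − rho), with df1 = m − 1 and df2 = (N − 2)(m − 1).

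- m = 2, N = 54: lambda = 0.0625 × 54 × 2 / 0.5 = 13.5, df 1 and 52, power 0.950.
- m = 3, N = 44: lambda = 0.0625 × 44 × 3 / 0.5 = 16.5, df 2 and 84, power 0.956.

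These are the smallest even N that reach 0.95 power. Power 0.80 would need 34 / 28, and 0.90 would need 46 / 36. So the stated figures reproduce at an implied power of 0.95, and one year's 30 or so students fall short of both.

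**2. Is 3:3 per year guaranteed?** With three schools per level per year, each level splits at best 2:1 or 1:2, so a year's arms can be 4:2, 3:3 or 2:4. The chance that the split differs between years depends on how equivalence is applied, which the plan does not say:

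| Reading | Chance that the split differs between years |
|---|---|
| Each year forced to 3:3 (a 2:1 at one level paired with a 1:2 at the other) | 0 |
| Each level 3:3 over the whole trial, Year 2 mirroring Year 1 | 2 of 4 = 50%, always 4:2 with 2:4 |
| Each level-by-year set split 2:1 or 1:2 independently | 10 of 16 = 62.5% |

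Of the 16 independent cases, 6 have equal shares, 8 differ by one school and 2 are 4:2 with 2:4.

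**3. How much of the year difference enters the arm contrast?** With equal school sizes it is the Year 2 share of the immediate arm minus that of the delayed arm, in absolute value.

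- 4:2 with 2:4: 4/6 − 2/6 = 0.333.
- Three and four immediate schools: 4/7 − 2/5 = 0.171. This gives 7:5 overall, so it can arise only under the independent reading.
- 3:3 in both years: 0.

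**4. Effect on the planned test.** The two-time-point test was simulated as a comparison of change scores: 60 students, 30 per year, SD of change 1 within year, students independent, no true effect, year term omitted. The year difference g is an assumption.

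| Split | g (SD) | Bias (SD) | Type I error |
|---|---|---|---|
| 4:2 then 2:4 | 0.3 | 0.10 | 0.063 |
| 4:2 then 2:4 | 0.5 | 0.17 | 0.09 |
| 4:2 then 2:4 | 1.0 | 0.33 | 0.18 |
| 3:3 each year | 0.3 | 0 | below 0.05 (0.045–0.048 across runs) |
| 3:3 each year | 0.5 | 0 | 0.043 |
| 3:3 each year | 1.0 | 0 | 0.028 |

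In the 3:3 case the extra residual variance is g²/4. At g = 0.3 this is 0.0225 on 1, about 2%, so the standard error rises about 1%. Power at f = 0.25 falls from 0.968 to 0.964 at g = 0.5 and to 0.947 at g = 1.0.

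**5. With the year term.** Bias is zero and type I error is 0.049–0.050 at every g tried. Power at N = 60 stays at 0.968 with 3:3 each year. With 4:2 then 2:4, arm and year are correlated at 1/3, the variance of the arm contrast rises by 1 / (1 − 1/9) = 1.125, and power is about 0.947.

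**The case against.** The arms run concurrently within each year on the same calendar, so any imbalance is chance, and over repeated allocations the bias is zero. The year difference is hypothetical, since the documents give no figure for it. At 0.3 SD the distortion is small even under the worst split considered here. Year of enrolment is also fixed before treatment, so an unequal year mix could be read as a baseline difference that the general covariate sentence already covers.

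Much of this stands, and it limits the point to a minor one. The covariate argument does not go far enough. That sentence does not name year and acts only once an imbalance has been seen and judged to matter. A year covariate without Year x Time also does not adjust the change that these tests compare.

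Three stronger inferences are tempting but unsupported:

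- A reader might take 62.5% as the chance of imbalance in this trial. It holds only under independent splits, which sit poorly with the stated aim of equivalent numbers per arm; the plan is equally open to 50% or zero.
- A reader who works with school means might put the loss of precision under 3:3 at about 9%: (1 + 4 × 0.05) / 5 = 0.24 with an assumed ICC of 0.05, and 0.0225 / 0.24 = 9.4%. The planned ANOVA is at student level, where the figure is about 2%.
- A reader might infer that omitting year generally inflates type I error. It does so only when the split differs between years; with 3:3 each year the test is conservative.

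**Conclusion.** The gap is real and minor. Allocation is done by year, the pooled Time X Group tests omit year, and nothing in the plan commits to Year x Time. The harm depends on the realised split: none to the estimate with 3:3 in each year, and one third of the year difference in change with 4:2 then 2:4. At an assumed 0.3 to 0.5 SD, the latter means 0.10 to 0.17 SD of bias and type I error of about 0.06 to 0.09.

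These figures assume equal group sizes, independent students and a year difference that the documents do not supply. School clustering is a separate matter. The Participants section, which counts six public schools over two years, leaves unclear whether the same schools return in Year 2; that does not alter the conclusion.

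The documents do not support saying that the trial's result is biased, or that the stated N is wrong. The N of 54 / 44 reproduces, and at N = 54 one lost degree of freedom moves power only from 0.9501 to 0.9499.

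**What to change.** State in the Aim 1 and Aim 2 Hypothesis 1 paragraphs that the models include year (2021-22 versus 2022-23) and Year x Time as the randomisation block, whatever imbalance is observed. If a re-randomisation test is used, permute within year. State whether equivalence of school numbers was applied within each year or over the trial, and report the immediate:delayed split of schools by year.

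The cost is a sentence or two in the plan, no new data and one degree of freedom. If the realised split is 4:2 then 2:4, the term also costs about two points of power when the years do not in fact differ (about 0.947 against 0.968). In that same split, omitting it would leave power at 0.87 if a 0.5 SD year difference worked against the treatment effect.
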